### **Procedures**

Participants will be recruited to participate in an intervention consisting of the smoking cessation + CPT-C or smoking cessation without concurrent CPT-C. Potential participants will complete a phone screen with study personnel to rule out those who are likely ineligible. Participants will be asked to attend a total of 15 study sessions, including a screening session, counseling and/or assessment sessions (a total of 12 counseling sessions and a 1-week post-treatment follow-up in each condition), and a 6 month follow-up to verify smoking abstinence and complete assessments.

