As part of the screening session, participants will be asked to fill out several questionnaires: PTSD symptom severity will be measured by the PTSD Checklist (PCL) (Weathers, Litz, et al., 2013), depressive symptoms will be measured by the Beck Depression Inventory (BDI-II) (Beck, Steer, & Brown, 1996), and perceived Self-Efficacy will be assessed with the Relapse Situation Efficacy Questionnaire (RSEQ) (Gwaltney, et al., 2001), and affective states will be assessed by the Positive and Negative Affect Schedule (PANAS) (Watson, Clark, & Tellegen, 1988). Information about minority, racial and marital status, medications, medical history, years of education and age will be collected. Participants' socioeconomic status will be measured using the Objective Socioeconomic Status measure (OSS; Adler, Epel, et al, 2000). General life satisfaction will be measured with the Quality of Life Inventory (Frisch et al., 1992). Information about nicotine dependence using the Fagerström Test of Nicotine Dependence (FTND) (Heatherton, Kozlowski, Frecker, & Fagerström, 1991), a stages of change measure (Prochaska and Diclemente, 1983), a question regarding motivation to quit smoking, and the Minnesota Nicotine Withdrawal Scale (MNWS) (Patten & Martin, 1996). General desire to smoke will be measured using the 32-item Questionnaire on Smoking Urges (QSU) (Tiffany & Drobes, 1991). Subjects will report about general smoking exposure history using the Smoking Exposure Questionnaire, and will report regarding electronic cigarette use on an internally designed measure. Participants will complete the Connor-Davidson Resilience Scale (CD-RISC). The CD-RISC is comprised of 25 5-point Likert-type items designed to measure an individual's range of abilities to manage different types of stress (Connor and Davidson 2003). In order to evaluate sleep quality and sleep problems, we will ask participants to complete the Pittsburgh Sleep Quality Index with

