### Assessments After Screening

Prior to each session, participants will complete questionnaires to assess psychiatric symptoms and smoking variables. These include the PTSD checklist (PCL), questions about smoking behavior in the past week, and the Beck Depression Inventory (BDI-II). In the final two sessions, participants will also complete the ASI, QOLI, TRGI, PSQI-A, CAPS, treatment satisfaction, Cook Medley Hostility Scale, e-cigarette use measure, and a question about current non-study psychotherapy. In session 8, participants will complete measures of treatment credibility and expectancy using the Reaction to Treatment Questionnaire (Borkovec & Nau, 1972). At the beginning and end of treatment, therapists will rate their level of allegiance to the therapy they are using with a single question asking "Which treatment do you think leads to better outcomes?" In the final treatment session, participants will also complete measures of SmokeFreeVet usability, and the nicotine dependence stages of change measure. In session 14 (after the final treatment session), participants will be interviewed with the CAPS.

Abstinence and relapse will be monitored by ED entries and at visits 7-14. Participants will provide breath samples for carbon monoxide (CO) analysis at every laboratory visit following their quit date. The first verification of smoking abstinence will occur on the morning following their quit date. Smoking abstinence will be obtained by self-report and verified by comparing CO levels to the level obtained at the baseline visit. The chart below lists the sliding scale of CO values that will be considered validating. At the six month follow-up visit, salivary cotinine will also be used to confirm self-reported

smoking abstinence. The formula in Table 1 below uses the participant's CO reading at the screening visit to determine the threshold that will be considered as confirming smoking abstinence after the quit date for each participant.

Table 1. Carbon Monoxide Thresholds for Validating Smoking Abstinence			
CO SCREENING	AM CO LIMIT		
		AM CO Limit after Overnight	
14-15	15	Abstinence	
16-18	16	AM CO Limit Formula: [14 + (.25 *	
19-21	17	(1.33 * (SCREENCO -14)))]	
22-24	18		
25-27	19		
28-30	20		
31-33	21		
34-36	22		
37-39	23		
40-42	24		
43-45	25		
46-48	26		
49-51	27		
52-54	28		
55-57	29		
58-60	30		
61-63	31		
64-66	32		
67	33		

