# **Data Analysis and Hypotheses:**

The following variables will be described for the sample as a whole: minority status, marital status, age, trauma exposure, negative affect level, PTSD symptom severity, nicotine dependence, mean pack years, nicotine cigarette brand, and mean number of cigarettes smoked daily.

Because one of the aims of this study is to assess the efficacy of the combined CPT-C and smoking intervention on smoking cessation, we will analyze these variables to determine whether they change over time.

- Compared to the smoking cessation alone protocol, the smoking cessation + concurrent CPT-C protocol will result in reduced frequency and intensity of PTSD symptoms.
- Compared to the smoking cessation alone protocol, the smoking cessation + concurrent CPT-C protocol will result in reduced depressive symptoms.
- 3) The smoking cessation + concurrent CPT-C protocol will result in decreased smoking rates, relative to published data on VA smoking cessation usual care.
- 4) Greater PTSD symptom reduction during the smoking cessation + concurrent CPT-C treatment will result in longer duration to smoking lapse and relapse.
- 5) Exploratory research question: Will use of automated text messaging as an adjunct to smoking cessation be feasible, and will it impact quit rates and symptom severity?

Hypothesis 1. Compared to the PTSD Coach and smoking cessation protocol, the CPT-C and smoking cessation protocol will result in reduced frequency and intensity of PTSD symptoms. The change in PTSD symptoms over time will be analyzed using repeated-measures ANOVA, utilizing data provided at baseline, post-treatment, and 6-months post-quit. We will evaluate the potential influence of several potential psychosocial covariates on smoking abstinence, including: 1) demographics (age, race, socioeconomic

status), 2) psychiatric variables (PTSD symptom severity, depression, substance abuse/dependence), 3) smoking variables (self-efficacy, motivation to quit, social support, smokers in social group), and 4) treatment process variables (therapeutic alliance, satisfaction with treatment, attendance at sessions, homework adherence).

Hypothesis 2. Compared to the PTSD Coach and smoking cessation protocol, the CPT-C and smoking cessation protocol will result in reduced depressive symptoms. Analysis procedures for Hypothesis 2 will be the same as those used for Hypothesis 1.

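### Hypotheses 1 and 2 use three visits and leave out the pre-session symptom scores, so the arm contrasts may be biased if dropout depends on response differently by arm

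*Combined protocol and SAP*

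**What the plan says.** The Assessments After Screening section schedules repeated symptom measurement: "Prior to each session, participants will complete questionnaires to assess psychiatric symptoms and smoking variables". It then names the instruments: "These include the PTSD checklist (PCL), questions about smoking behavior in the past week, and the Beck Depression Inventory (BDI-II". Both scales are also given at screening, and the Procedures section sets the visit count: "Participants will be asked to attend a total of 15 study sessions". Table 2 lists questionnaires in both arms at sessions 2 to 13 and again at session 15, but none at session 14.

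The Data Analysis and Hypotheses section analyses Hypothesis 1 by repeated-measures ANOVA, "utilizing data provided at baseline, post-treatment, and 6-months post-quit". For depression it adds: "Analysis procedures for Hypothesis 2 will be the same as those used for Hypothesis 1". Nowhere do the session scores enter either hypothesis, whether as outcome, auxiliary variable or input to imputation.

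Hypothesis 1 says only that the combined treatment "will result in reduced frequency and intensity of PTSD symptoms", without naming a scale. The CAPS is scheduled at screening, session 14 and session 15, and those visits match the three analysis points. The BDI-II is the only depression scale named.

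The protocol foresees incomplete data: dropout (Recruitment), loss of contact (Intervention Protocol) and missed appointments (CPT-C Post Follow-Up). It states no dropout rate, analysis population or missing-data method.

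**The concern.** The scores left out are those that describe the course of people who do not reach the end of treatment. A participant who leaves after session 6 has a baseline and five later scores (sessions 2 to 6). In the three-visit data only the baseline remains. A classical repeated-measures ANOVA, which needs complete cases, then drops that person. A likelihood model on the same three visits keeps the baseline and predicts the rest from people who stayed.

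The Background section reports that in the cited dismantling study the PTSD improvement had appeared by session six, so on the protocol's own account mid-treatment scores should be informative. Visit burden also differs: Table 2 shows mostly 1 hr 45 min per visit with CPT-C against 55 min without. Different reasons for leaving in the two arms are therefore plausible. The between-arm change in PTSD and depression, listed first and second under the primary aim, is what is at stake.

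**Working it through.** **Scores scheduled and used.** With 15 sessions and one score per session, 3 are analysed and 12/15 = 80% are not. If none is taken at session 14, 14 are scheduled and 11/14 = 79% are unused. The interim scores number 12 (sessions 2 to 13) if session 14 supplies the post-treatment value, or 11 (sessions 2 to 12) if session 13 does. The session 2 score precedes the first treatment.

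**No figure in the plan to reproduce.** The documents give no effect size, SD, dropout rate or allocation ratio. All simulation inputs below are assumptions.

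**Simulation A.** 30 per arm; true post-treatment difference −9 PCL points; dropout 36% versus 14%, driven by the last score; 500 trials; multivariate-normal likelihood.
- Full data: −8.7.
- Baseline and post-treatment only: −10.6, RMSE 4.6. The excess is (10.6 − 8.7)/8.7 = 22% against full data, or (10.6 − 9)/9 = 18% against the truth.
- With every second pre-session score added: −8.9, RMSE 4.2.
- With 24% versus 32% dropout there was little bias either way, and the SE fell from 4.23 to 4.05, that is (4.23 − 4.05)/4.23 = 4%.

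**Simulation B.** N = 50, 1:1; 15 visits; SD 1; correlation icc + (1 − icc) × rho^lag for (icc, rho) = (0.3, 0.9), (0.5, 0.8), (0.5, 0.6); 700 replicates per cell; covariance treated as known, which is a best case. Negative bias favours CPT-C. The Monte Carlo error of a bias is about 0.33/√700 = 0.012.

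Post-treatment bias in SD units for (0.5, 0.8), heavier dropout setting:

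| Dropout mechanism | Lost, control / CPT-C | True effect | Completers | Likelihood, 3 visits | Likelihood, 15 visits |
|---|---|---|---|---|---|
| Random | 35% / 36% | 0 | 0.000 | +0.004 | +0.006 |
| Response-driven, same in both arms | 42% / 42% | 0 | +0.018 | +0.021 | +0.018 |
| Response-driven, same in both arms | 42% / 34% | 0.5 | +0.058 | +0.035 | −0.021 |
| Response-driven in CPT-C only | 35% / 42% | 0 | −0.269 | −0.163 | +0.020 |
| Response-driven in CPT-C only | 35% / 34% | 0.5 | −0.230 | −0.155 | −0.010 |

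Across all three correlation settings, with no true effect and response-driven dropout in CPT-C only:
- completers: bias 0.18 to 0.32 SD, type I error 10 to 18%;
- likelihood on three visits: 0.11 to 0.21 SD, 6 to 9%;
- likelihood on 15 visits: within 0.02 SD, 4 to 6%.

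**Precision under random dropout.** Completers' standard errors were 3 to 6% larger than with all visits at 20% dropout, and 7 to 14% larger at 35%. Part of that gain comes from changing the model rather than adding scores. In the first row of the table the SDs of the estimate were 0.356, 0.330 and 0.313, so completers lose 0.356/0.313 = 1.14, of which the three-visit likelihood model still loses 0.330/0.313 = 1.05.

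**Equal rates are not reassurance.** In the last row the arms lose 35% and 34%, yet the three-visit bias is −0.155. What matters is whether the reason for leaving differs between arms.

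**The case against.** Five counter-arguments deserve weight.

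1. **Instrument.** A reader might infer that Hypothesis 1 throws away PCL outcome data. The documents do not establish that. Its three time points match the CAPS schedule, and its wording on frequency and intensity differs from the severity language used for the PCL at screening. If the CAPS is meant, no CAPS visit is discarded. This stands, and the fix must be conditional on it.
2. **Direction.** A reader might also infer that the plan overstates the benefit of CPT-C. That needs non-responders to leave mainly from CPT-C. The Background section describes dropout from the 12-session protocol as fairly low, and comparator participants are offered CPT-C only after the 6-month visit, which could prompt dissatisfied controls to leave. A mirror-image run (30 per arm, true −9, SD 14, known covariance, 36% control and 14% CPT-C dropout) gave about −6.5 from a three-visit likelihood model, an understatement of (9 − 6.5)/9 = 28%. This stands.
3. **Model.** Adding visits to a classical repeated-measures ANOVA would not help, because it drops incomplete cases. The fault is not independent of the model, and the model has to change first. This stands.
4. **Fidelity of the simulations.** Simulation A omits the 6-month visit. When half of those who stopped were assumed to return at 6 months, a three-visit model gave −10.5 against −10.8 for two visits, so the extra visit helps only slightly. In Simulation A dropout depends on observed scores, so a model containing those scores is favoured by construction. That limits the claim to dropout explained by what was measured.
5. **Size.** Outside differential, response-driven dropout the gain is a few percent in precision. This stands.

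What survives is that scheduled, relevant data are left out when the plan foresees dropout and says nothing on handling it.

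**Conclusion.** The concern holds as a conditional weakness that should be corrected. For Hypothesis 2 it applies in full. For Hypothesis 1 it applies in full if the PCL is the outcome, and as a missed auxiliary variable if the CAPS is.

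The size depends on the dropout mechanism. If response-driven dropout is confined to one arm, the simulations suggest 0.11 to 0.21 SD of bias from a three-visit likelihood model and 0.18 to 0.32 SD from completers under the null, towards or away from CPT-C according to the arm affected. If the mechanism is the same in both arms there is about no bias under the null, and completers' estimates are attenuated by 0.05 to 0.08 SD at a true effect of 0.5 SD. If dropout is random, only precision is lost. These figures rest on assumed dropout, correlation and allocation, and the near-complete removal of bias rests on a known covariance. The documents do not show that dropout will differ by arm, so no single figure should be read as the expected bias of this trial.

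**What to change.** Amend the analysis of Hypotheses 1 and 2 as follows.

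- **Model.** Replace the repeated-measures ANOVA with a likelihood-based mixed model in all randomised participants. Include all pre-session BDI-II scores (and PCL scores, if the PCL is the Hypothesis 1 outcome). Keep visit categorical by arm, and still take the arm contrasts at post-treatment and 6 months.
- **Outcome.** Name the Hypothesis 1 instrument. If it is the CAPS, keep its three visits and bring in the session PCL as auxiliary variables through a joint model or multiple imputation.
- **Covariance.** Name a structured or random-slope form. The Population section's figures of fifty and seventy imply about 25 to 35 per arm if allocation is 1:1. An unstructured matrix on 15 visits needs 15 × 16/2 = 120 parameters, which is too many. The form must allow for the long gap before the 6-month visit. Using every second session score is a simpler fallback, and it was enough in Simulation A.
- **Post-treatment visit.** State which session supplies the post-treatment PCL and BDI-II, and reconcile Table 2's session 14 with the text on questionnaires at each session.
- **Sensitivity.** Add an analysis allowing for not-at-random dropout.

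The cost is SAP wording and a larger model on data already scheduled, with no added visits. The downsides are more covariance assumptions, no help for people who leave before any post-baseline score, and no protection against dropout that depends on unobserved outcomes.

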Heavy smokers (as defined by CO readings greater than 30 ppm) will be prescribed 42 mg. patches. Two weeks after their quit date, participants will lower the dose of the prescribed nicotine patch (i.e., participants receiving 21 mg initially will lower to 14 mg, and those receiving 42 mg will lower to 21 mg). At three weeks after the quit date, any participant who initially received the 42 mg patch will lower the patch dose further to 14 mg. At four weeks post-quit, all participants will replace the 14 mg patch with a 7 mg patch, to be worn for two weeks. All NRT, including both the patch and rescue method, will end 6 weeks after the target quit-smoking date. If any participant has been unable to maintain abstinence during the follow-up period, he/she may be allowed to reinitiate NRT during the follow-up period in order to make a renewed quit attempt. Dosage of NRT will be decided by the study physician at this time point, and will depend upon the participant's most recent smoking patterns and CO reading.

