Hypothesis 3. The CPT-C and smoking cessation protocol will result in decreased smoking rates, relative to published data on VA smoking cessation usual care. An outcome variable denoting the proportion of subjects abstinent at Week-6 will be regressed on the group proxy and included covariates using standard logistic regression procedures. A secondary analysis will explore cessation rates at the 6-month follow-up.

Hypothesis 4.-The level of PTSD symptom reduction during the intervention will be related to longer latency to relapse. PTSD symptom change scores will be used to evaluate the degree of PTSD symptom reduction. We will fit Cox proportional hazard regression models to the data to evaluate effects of PTSD symptom reduction on the time to relapse.

Hypothesis 5. Exploratory research question: Will use of automated text messaging as an adjunct to smoking cessation be feasible, and will it impact quit rates and symptom severity? This will be evaluated by examining proportion of participants choosing to utilize text messaging, retention rates, and usage rates.

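### The covariates listed for smoking abstinence include no measure of baseline smoking level, although screening CO is collected, sets each participant's verification limit, and could be unbalanced by chance between small arms

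*Combined protocol and SAP*

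**What the plan says.** The covariates are introduced in the Hypothesis 1 paragraph of Data Analysis and Hypotheses, although they are aimed at quitting: "We will evaluate the potential influence of several potential psychosocial covariates on smoking abstinence, including" four groups. The groups are demographics (3 items), psychiatric variables (3), smoking variables (4) and treatment process variables (4). The smoking group is "smoking variables (self-efficacy, motivation to quit, social support, smokers in social group".

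Under Hypothesis 3, Week-6 abstinence "will be regressed on the group proxy and included covariates using standard logistic regression procedures". The section does not say which covariates are included or what the group term compares. The hypothesis itself reads: "The CPT-C and smoking cessation protocol will result in decreased smoking rates, relative to published data on VA smoking cessation usual care". Cessation at six months is a secondary analysis.

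Baseline smoking level is measured. The Screening Session section records CO, salivary cotinine and cigarettes per day, and adds "Information about nicotine dependence using the Fagerström Test of Nicotine Dependence (FTND". In the analysis section, dependence, pack years and cigarettes per day are described for the whole sample and examined for change over time. They are not named as covariates, and screening CO is not mentioned there.

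CO also enters the outcome and the treatment. Under Assessments After Screening, the Table 1 formula "uses the participant's CO reading at the screening visit to determine the threshold" that confirms abstinence; the printed limits run from 15 to 33 ppm. Under Nicotine Replacement Therapy: "Heavy smokers (as defined by CO readings greater than 30 ppm) will be prescribed 42 mg. patches". The Intervention Protocol section describes a centrally generated sequence and mentions no stratification.

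**The concern.** A baseline measure of smoking level is a natural adjustment variable for a quit outcome, and this plan has several in hand. Screening CO stands out because it is tied to the outcome by design: a participant with a higher screening reading is allowed a higher CO limit afterwards. It probably also bears on the 42 mg patch assignment, since screening is the only pre-quit CO reading described.

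With 25 to 35 participants per arm and no stated stratification, the arms could differ noticeably in smoking level by chance. An unadjusted comparison would carry that difference into the estimated effect on quitting. If no baseline smoking covariate is fixed in advance, any later adjustment is open to the charge that it was chosen after the data were seen.

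**Working it through.** The documents give no alpha, power, expected abstinence rate, covariate correlation or allocation ratio, so there is no stated figure to reproduce. The calculations below use N = 50 (the minimum enrolment goal) and N = 70 (the recruitment figure), both from the Population section. All other inputs are assumptions.

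**Size of the listed model.** Covariates: 3 + 3 + 4 + 4 = 14. With the group term there are 15. At assumed abstinence of 15% to 35%, the number abstinent is N × rate:
- N = 50: 7.5 to 17.5, or 7.5/15 = 0.5 to 17.5/15 = 1.2 events per term.
- N = 70: 10.5 to 24.5, or 10.5/15 = 0.7 to 24.5/15 = 1.6 events per term.

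The full list is already far more than the data can carry.

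**Chance imbalance in the share above 30 ppm.** Assume 1:1 allocation with n = N/2 per arm and prevalence p. The numbers above the cut, X1 and X2, are independent Binomial(n, p), and the quantity is P(|X1 − X2|/n ≥ 0.15). With n = 25, 0.15 × 25 = 3.75, so a difference of 4 or more counts. With n = 35, 0.15 × 35 = 5.25, so 6 or more counts. Exact results:

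| Assumed prevalence | N = 50 | N = 70 |
|---|---|---|
| 20% | 0.213 | 0.099 |
| 30% | 0.279 | 0.151 |
| 40% | 0.312 | 0.179 |

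**The same question on a continuous scale.** The between-arm difference in a standardised baseline measure has SE = √(4/N), which is 0.28 SD at N = 50 and 0.24 SD at N = 70. The chance of a difference of at least 0.25 SD is 38% and 30%. For at least 0.5 SD it is 7.7% and 3.6%.

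**What an imbalance does to the estimate.** Logistic data were simulated (3,000 runs per setting) with abstinence of 20% v 45% and one standardised covariate, whose odds ratio per SD was varied from 1.0 to 2.5. For odds ratios of 1.5 to 2.5, the unadjusted risk difference moved by 0.08 to 0.17 per SD of imbalance. A 0.5 SD imbalance therefore shifts it by about 4 to 8 points. At N = 70 and an odds ratio of 2.0, adjustment took the slope from −0.13 to about 0.

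**Power, unadjusted to adjusted, from the same simulations (two-sided 0.05):**

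| Covariate OR per SD | N = 50 | N = 70 |
|---|---|---|
| 1.0 | 0.48 to 0.47 | 0.60 to 0.59 |
| 1.5 | 0.46 to 0.46 | 0.61 to 0.63 |
| 2.0 | 0.48 to 0.49 | 0.63 to 0.66 |
| 2.5 | 0.47 to 0.52 | 0.61 to 0.67 |

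The change is about −1 to +6 points. A separate logistic simulation at 30% v 50% gave about −1 to +3 points at N = 50 and 0 to +6 at N = 70. The mean standard error of the log odds ratio rose in every setting, for example from 0.57 to 0.61 at N = 70 with an odds ratio of 2.0. Any gain therefore shows in the test or in a standardised risk difference, not in that standard error.

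**The case against.** The strongest reply is that the plan does not exclude this adjustment. The list is introduced as examples, is confined to psychosocial factors, and the Hypothesis 3 covariates are left open. A reader might infer that the plan rules out CO or FTND; it only fails to name them. That stands, and it is why the point concerns pre-specification.

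Second, Hypothesis 3 is worded against published usual-care data. Imbalance between randomised arms matters only if the group term means the two arms, which is not stated. This also stands and limits the fix.

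Third, the net association of CO with verified abstinence is unknown. A more lenient limit would push verified abstinence up with CO, while heavier smoking would plausibly push it down. At six months a fixed cotinine cut of 10 ng/ml also applies, which weakens the threshold argument there. One linear term will not capture a step at 30 ppm.

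Fourth, imbalance should be kept in proportion. If quit rates differed by 20 points across the 30 ppm cut (an assumption), a 15-point imbalance shifts the risk difference by 0.15 × 0.20 = 3 points. The standard error at N = 70 with 30% v 50% is √(0.30 × 0.70/35 + 0.50 × 0.50/35) = 11 points. Randomisation already accounts for such chance differences in the type I error, so it would be too strong to say that the unadjusted model is biased towards CPT-C.

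Finally, adding a term to a 15-term model has a cost. It does, so the covariate should replace something.

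**Conclusion.** The point holds as a minor improvement. Baseline smoking level is collected but not named as an abstinence covariate, screening CO helps define the verified outcome, and no stratification is stated. Under 1:1 allocation and 20% to 40% prevalence, a 15-point imbalance above 30 ppm has probability 21% to 31% at N = 50 and 10% to 18% at N = 70. The case rests mainly on correcting such an imbalance by a rule fixed in advance.

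Three stronger readings are not supported:
- A reader might expect a power gain of about 10 points. That comes from multiplying the variance by 1 − ρ² with ρ = 0.5 (at N = 70 and 30% v 50%, 41% to 51%). That rule is for a continuous outcome, and the documents give no ρ. The logistic range is about −1 to +6 points.
- A reader might infer that CO sets every participant's patch dose. It bears only on the 42 mg assignment, and the text does not say which reading counts. The 14 mg example depends on cigarettes per day, and the study physician determines the initial level.
- CO and FTND might be called baseline values of the outcome. The outcome is binary abstinence and everyone enters smoking at least ten cigarettes a day, so they are candidate predictors.

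The sizes depend on assumed abstinence rates, covariate strength, alpha and allocation.

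**What to change.** State what the group term in the Hypothesis 3 model compares. If it is the two randomised arms, name screening CO as a single linear covariate in the between-arm abstinence models at Week 6 and six months, with FTND substituted for it in a sensitivity analysis. Put it in place of weaker entries among the 14 rather than on top of them. The four treatment process variables are natural ones to remove from the treatment-effect model, because they arise after randomisation. If the comparison is with published usual-care rates, this adjustment does not apply.

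The cost is a sentence or two in the analysis section and one degree of freedom. No new data are needed. If CO proves weakly prognostic, there will be little or no gain and possibly a loss of about one point of power.

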## **Objectives:**

The primary aim of the proposed study is to evaluate the integration of CPT-C and smoking cessation treatment in an individual 12-session PTSD protocol as compared to a protocol including the same smoking cessation treatment for individuals with PTSD, but without CPT-C. This intervention will be evaluated with the following hypotheses:

- Compared to the smoking cessation alone protocol, the smoking cessation + concurrent CPT-C protocol will result in reduced frequency and intensity of PTSD symptoms.
- 2) Compared to the smoking cessation alone protocol, the smoking cessation + concurrent CPT-C protocol will result in reduced depressive symptoms.
- 3) The smoking cessation + concurrent CPT-C protocol will result in decreased smoking rates, relative to published data on VA smoking cessation usual care.
- 4) Greater PTSD symptom reduction during the smoking cessation + concurrent CPT-C treatment will result in longer duration to smoking lapse and relapse.
- 5) Exploratory research question: Will use of automated text messaging as an adjunct to smoking cessation be feasible, and will it impact quit rates?

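### The Hypothesis 3 abstinence model does not name its covariates, and the plan's only covariate list for abstinence includes variables that arise after randomisation

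*Combined protocol and SAP*

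**What the plan says.** All of this is in the combined protocol and SAP.

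- **Data Analysis and Hypotheses, Hypothesis 3.** The outcome is abstinence at Week 6, which "will be regressed on the group proxy and included covariates using standard logistic regression procedures". No covariate is named there. The hypothesis itself is worded as a comparison "relative to published data on VA smoking cessation usual care".
- **Data Analysis and Hypotheses, Hypothesis 1.** After the repeated-measures ANOVA for PTSD symptoms, the paragraph turns to a different outcome: "We will evaluate the potential influence of several potential psychosocial covariates on smoking abstinence, including" four groups of variables. These are demographics (3), psychiatric variables (3, among them PTSD severity and depression), smoking variables (4) and "treatment process variables (therapeutic alliance, satisfaction with treatment, attendance at sessions, homework adherence" (4). No time point is given for any of them, and no selection rule.
- **Screening Session and Intervention Protocol.** PCL and BDI-II are completed at screening. Randomisation follows for those found eligible.
- **Assessments After Screening.** Symptom measurement is repeated throughout treatment: "Prior to each session, participants will complete questionnaires to assess psychiatric symptoms and smoking variables". PCL and BDI-II are both named among the instruments used at these visits. Treatment satisfaction is collected in the final two sessions.
- **Objectives.** Hypotheses 1 and 2 predict that the smoking cessation plus "concurrent CPT-C protocol will result in reduced frequency and intensity of PTSD symptoms", and likewise that the "concurrent CPT-C protocol will result in reduced depressive symptoms".

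**The concern.** The Hypothesis 3 model is the only stated model with an arm term for abstinence. Its covariates must come from somewhere, and the plan offers one list only. Four of the listed variables cannot exist before treatment starts. Two more, PTSD severity and depression, have both a pre-randomisation value and a series of later values, and the plan itself predicts that the arms will differ on the later ones.

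A covariate that treatment can change does one of two things to the group coefficient. If it carries part of the treatment effect, adjusting for it removes that part. If it shares an unmeasured cause with abstinence, adjusting for it can create an arm difference where none exists. In both cases the comparison loses the protection of randomisation. An unnamed covariate set also leaves the choice open until the results are known.

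**Working it through.** **1. Does any other text settle the covariates?** No. There is no second covariate list for abstinence, no restriction to baseline values in Hypothesis 3, and no statement that process variables stay out of that model.

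**2. Could the whole list be entered?** The list has 3 + 3 + 4 + 4 = 14 variables; with group, and race as one term, that is 15 coefficients. The Population section gives 70 to be recruited and an enrolment goal of at least 50. Abstinence is not given; assume 10% to 40%.

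- N = 50: 5 to 20 events, so 5/15 = 0.33 to 20/15 = 1.33 events per coefficient.
- N = 70: 7 to 28 events, so 7/15 = 0.47 to 28/15 = 1.87.

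The full list could not be fitted reliably, so some selection would be made, and the plan does not say how.

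**3. How large could the distortion be?** The plan has no figure to reproduce. All inputs here are assumptions: control abstinence 30%, 1:1 allocation, a covariate M scored so that higher is better. The odds ratios are large-sample values obtained by numerical integration.

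*Case A: M carries the whole effect.* M = d × arm + N(0,1); logit P(abstinent) = c + g × M, with c set to give 30% in controls. Total OR = [p1/(1 − p1)] / [0.30/0.70].

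| Arm shift d (SD) | Log-OR per SD, g | p1 | Total OR | OR adjusted for M |
|---|---|---|---|---|
| 0.2 | 0.4 | 0.317 | 1.08 | 1.00 |
| 0.5 | 0.8 | 0.379 | 1.42 | 1.00 |
| 0.8 | 0.8 | 0.430 | 1.76 | 1.00 |

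The last column is true by construction: under full mediation, adjusting for the mediator leaves nothing. The table shows what would be lost and is no evidence that it would be.

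*Case B: M carries part of the effect.* With a direct OR of 1.50 added, total ORs for the same three rows are 1.60, 2.03 and 2.51. Each becomes 1.50 after adjustment.

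*Case C: no treatment effect, shared cause.* U ~ N(0,1); M = d × arm + k × U + N(0,1); logit P = c + k × U; true OR 1.00. With the arm shift in total SD of M, the adjusted OR runs from 0.98 (shift 0.2, k = 0.3) to 0.60 (shift 0.8, k = 1.0). With no arm shift it is 1.00 for every k.

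**4. Does adjusting for the screening value avoid this?** Take Case A with a screening score correlated 0.3 to 0.7 with the later score. Adjusted for the screening score, the ORs are 1.08, 1.43 to 1.45, and 1.77 to 1.82. The effect is kept; the slight rise is the usual behaviour of a logistic model with a prognostic covariate. Adjusted for the later score, each is 1.00.

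**5. Against sampling error.** The standard error of the log-OR is √[1/(n·p0·q0) + 1/(n·p1·q1)], with n per arm.

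- n = 25, 30% in both arms: √[2/(25 × 0.21)] = 0.62.
- n = 35, 30% against 43%: √[1/7.35 + 1/8.58] = 0.50.

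The 95% limits are therefore the OR multiplied or divided by about 2.7 to 3.4. The 1.08-to-1.00 shift (0.08 on the log scale) is trivial beside that; the 1.76-to-1.00 shift (0.57) is about one standard error.

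**The case against.** The strongest reply is that the link is inferred. Hypothesis 3 does not say that its covariates are the Hypothesis 1 list, and evaluating the influence of variables on abstinence is ordinary wording for a separate predictor analysis. This stands: a reader might infer that the plan commits to adjusting the arm comparison for post-randomisation variables, and the documents do not say so. They permit it and point to no other list.

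Other limits also stand.

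- A reader might take the listed PTSD and depression values to be on-treatment scores. Screening values fit better. The list keeps process variables in their own group and puts PTSD and depression beside substance abuse/dependence, which is determined by clinical interview as part of screening. Hypothesis 4 uses different terms, symptom reduction and change scores, for later change. The repeated PCL and BDI-II leave the time point open, but no more.
- A reader might say that the plan's own theory runs from CPT-C through PTSD to abstinence. Hypotheses 1 and 2 do predict arm differences in symptoms. Hypothesis 4, however, concerns time to lapse and relapse, and the Objectives word it within the combined treatment. It is neither about Week-6 abstinence nor a between-arm claim, so extending it is inference.
- Hypothesis 3 names published usual care as comparator, and the group proxy is not defined. Whether the coefficient is meant as the randomised effect is thus unsettled. That mismatch is a separate matter.
- No instrument for alliance or homework adherence is visible, so two of the four process variables may not exist as data.

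**Conclusion.** The point holds in conditional form. It is certain that the Hypothesis 3 covariates are unnamed and that the only list for abstinence contains variables arising after randomisation. If that list feeds the model, the group coefficient does not estimate the randomised effect on abstinence. For PTSD severity and depression, the defect is only that the time point is not fixed.

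The documents give no basis for a size. On assumed inputs the distortion goes from negligible (1.08 to 1.00) to large (1.76 to 1.00, or a true 1.00 read as 0.60). With no true effect it is zero when the covariate does not differ by arm. These figures rest on the assumed 30% control rate, arm shifts and covariate strengths, and the full-mediation values follow from the model by construction. This is a cheap improvement to the SAP and does not show that the planned analysis is biased.

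**What to change.** Under Hypothesis 3, add: *The group term is adjusted only for the following covariates measured at the screening visit: [short list, for example PCL and BDI-II]. No value measured after randomisation enters this model.* The final list should be written out, since a placeholder would leave the gap open. It should be short: with group plus two covariates there are 3 coefficients, so at an assumed 30% abstinence there would be 15/3 = 5 (N = 50) to 21/3 = 7 (N = 70) events per coefficient.

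In the covariate text under Hypothesis 1, add: *Treatment-process variables and on-treatment symptom scores, where collected, are examined only in a separate exploratory, non-randomised analysis of predictors of smoking abstinence.*

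The cost is two sentences and a decision on the list. PCL and BDI-II are already collected at screening, so no new data are needed. The downside is that process variables no longer inform the treatment comparison; they can still be studied in the exploratory analysis.
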